### 12.9.2 Secondary variables

IGA-response will be analyzed using a longitudinal mixed model for binary outcomes (GENMOD). The model will include Treatment Arm as a factor and respective baseline value as a covariate, with the treatment-by-visit interaction term as a random effect to account for missing data. The primary analysis will be based on the FAS, and repeated for the PPS as a supportive sensitivity analysis. The models will also allow the estimation of the response percents at each on-study visit in addition to Week 8. The shift from Week 8 to Week 10 will also be of interest to assess relapse once off study drug.

Change from baseline endpoints (IGA, DLQI, POEM, PGI-S and PGI-C) will be analyzed using mixed model with repeated measures (MMRM) with Treatment Arm as a factor and respective baseline value as a covariate, with the treatment-by-visit interaction term as the random effect to account for missing data. The secondary efficacy analyses will be based on the FAS only.

In addition, a hierarchical testing sequence will be adopted, giving a pre-defined testing order for multiple efficacy endpoints as follows: NRS, EASI, IGA, IGA response, PGI-S, PGI-C, DLQI and POEM.

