2.2.8 Statistical Hypotheses

The original null hypothesis (H_0) for each analysis is the equality of the means for the three treatment groups. A global test was to be performed across all three treatment groups. The test will still be performed

The revised primary focus will be the separate comparisons of the two DS107 concentrations vs. vehicle control using a Dunnett’s correction (two-sided 97.4% confidence intervals and two-sided $p=0.026$) to reach statistical significance. The null hypotheses are the pairwise comparisons of the equality of the two DS107 concentrations vs. vehicle. Dunnett’s procedure will be used to adjust for the multiple comparisons. The overall 5% Type I error rate is controlled for by the Dunnett’s correction for multiple comparisons.

Testing between the two active groups will be considered as descriptive statistics.

All statistical testing will be two-sided; global tests will be performed at the 0.05 level while all pairwise DS107 comparisons vs vehicle will be performed at the 0.026 level.

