2.2.12.4 Controlling Type I error

Dunnett's test will be used to provide for simultaneous comparisons of each DS107 dose vs. vehicle by allowing two-sided $p=0.026$ per dose comparison.

No multiplicity adjustment is necessary for the primary and co-primary endpoints as the Type I error rate will not be affected because both must be met for study success. A hierarchical testing sequence methodology will be applied to the second and exploratory endpoints in order to control the overall type 1 error. Table 2 provides the order of testing for each active dose group compared to the vehicle group for the secondary and exploratory efficacy endpoints; these will each be global tests across all post-baseline outcomes excluding Week 10. Each of these tests will be at the 0.05 significance level. A test will be considered statistically significant only if the corresponding test has a p -value <0.05 and all previous tests (as determined by the testing order defined in Table 2) have a p -value <0.05 .

Table 2. Hierarchical Testing Sequence for Secondary and Exploratory Endpoints

Testing Order	Endpoint	Efficacy Endpoint
1	Secondary	Change in NRS from baseline
2	Secondary	Proportion achieving a reduction of at least 2.7 points in NRS
3	Secondary	Change in EASI from baseline
4	Secondary	Proportion achieving an IGA score of 0 or 1 and a decrease of at least 2 points in IGA
5	Secondary	Proportion achieving a decrease of at least 2 points in IGA
6	Secondary	Change in IGA from baseline
7	Exploratory	Change in DLQI from baseline
8	Exploratory	Change in POEM from baseline
9	Exploratory	Change in PGI-S from baseline
10	Exploratory	Change in PGI-C from baseline

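### The secondary and exploratory hierarchy runs at 0.05 for each dose and does not depend on the co-primaries, so it does not control the overall type I error as the SAP claims

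*SAP*

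**What the plan says.** SAP 2.2.12.4 gives the purpose of the sequence: "A hierarchical testing sequence methodology will be applied to the second and exploratory endpoints in order to control the overall type 1 error". Four features of the text matter.

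- **Unit of testing.** "Table 2 provides the order of testing for each active dose group compared to the vehicle group". There are therefore two chains, one for each dose.
- **Level.** "Each of these tests will be at the 0.05 significance level". The same section opens by allowing 0.026 for each dose comparison, and SAP 2.2.8 says that "all pairwise DS107 comparisons vs vehicle will be performed at the 0.026 level". SAP 2.2.8 also says "The overall 5% Type I error rate is controlled for by" the Dunnett correction.
- **Meaning of global.** The section says "these will each be global tests across all post-baseline outcomes excluding Week 10", which describes pooling over visits.
- **Look-back.** A row counts as significant if its own p-value is below 0.05 and so is that of "all previous tests (as determined by the testing order defined in Table 2"). Table 2 begins with the secondary NRS endpoint. The Week 8 co-primary tests are not rows in it, and no other SAP sentence makes entry depend on them.

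Protocol 12.9.2 has its own sequence, "giving a pre-defined testing order for multiple efficacy endpoints as follows: NRS, EASI, IGA, IGA response, PGI-S, PGI-C, DLQI and POEM". SAP Table 2 runs differently: NRS change, NRS responders (2.7 points), EASI change, two IGA responder endpoints, IGA change, DLQI, POEM, PGI-S, PGI-C.

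**The concern.** A fixed sequence protects the error rate along one chain. It does nothing about running two chains side by side, which is why the Dunnett level of 0.026 per dose was adopted for the co-primaries. Returning to 0.05 per dose for the rest gives that protection up. A secondary result with p between 0.026 and 0.05 would also be called significant while the 97.4% interval prescribed in SAP 2.1 still included zero.

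The missing gate is a separate defect. Row 1 is NRS change over the post-baseline visits other than Week 10. A dose that fails the Week 8 NRS test can therefore come back with a formally significant NRS secondary, and then continue down nine more rows.

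Finally, a fixed sequence is valid only if one order is set in advance. With two published orders, a reader cannot tell which results were confirmatory. At stake is the credibility of every secondary and exploratory claim for both doses.

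**Working it through.** **Inputs.** Allocation 1:1:1 (SAP Study Design summary). Level 0.026 per dose, two-sided (SAP 2.2.8). Level 0.05 per row (SAP 2.2.12.4). Differences 1.22 (NRS) and 2.60 (EASI), DS107 SDs 2.49 and 4.45, vehicle SDs 3.04 and 7.11, n = 100 per arm, power 80% (SAP 2.2.9). The documents give no correlations between endpoints, so 0, 0.5 and 0.8 are assumed.

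**1. The plan's own figure.** With an unequal-variance (Satterthwaite) t-test at 0.026 and 80% power, the smallest n per arm is 99 for NRS and 100 for EASI. At n = 100 the power is 80.5% and 80.2%. The stated 100 reproduces. At 0.05 both would need only 83, so the design does rest on 0.026.

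**2. Two doses at one null step.** Let c = z(1 − α/2). The error is 1 − P(|Z1| < c, |Z2| < c), with Z1 and Z2 bivariate normal. Equal variances and 1:1:1 allocation give correlation 0.5.

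- α = 0.026, c = 2.226: error 0.0483
- α = 0.05, c = 1.960: error 0.0907

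With unequal variances the correlation is σ2²/(σ1² + σ2²):

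- NRS: 9.2416/15.4417 = 0.598, error at 0.05 = 0.088
- EASI: 50.5521/70.3546 = 0.719, error at 0.05 = 0.083

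Under independence the error is 1 − 0.95² = 0.0975. Every case exceeds 0.05.

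**3. Co-primaries and row 1 together.** This was simulated with 400,000 runs per scenario. The co-primaries are tested at 0.026 per dose, the correlation between doses is 0.5, and a truly effective co-primary is taken as always rejected. Row 1 is null throughout. Ranges run over the assumed endpoint correlations. Gated means that a dose enters only after rejecting both co-primaries.

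| Truth | 0.05, ungated (SAP) | 0.05, gated | 0.026, ungated | 0.026, gated |
|---|---|---|---|---|
| All null | 0.092–0.095 | 0.001–0.020 | 0.049–0.056 | 0.001–0.020 |
| EASI effective, NRS null | 0.111–0.135 | 0.049 | 0.077–0.094 | 0.049 |
| Both co-primaries effective | 0.091 | 0.091 | 0.048 | 0.048 |

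Hand check of the second line at zero endpoint correlation: 1 − (1 − 0.0483)(1 − 0.0907) = 0.135 at 0.05 ungated, and 1 − (1 − 0.0483)² = 0.094 at 0.026 ungated. Both agree with the simulation.

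Gating alone leaves 0.091 in the third line. Changing the level alone leaves 0.077 to 0.094 in the second. Both changes are needed.

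**4. Power cost.** A test with 80% power at 0.05 has Φ(1.960 + 0.842 − 2.226) = Φ(0.576), or about 72%, at 0.026.

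**The case against.** The strongest defence lies in the word global. SAP 2.2.8 assigns 0.05 to global tests and 0.026 to pairwise ones, and it uses global for a test across all three arms. If the Table 2 rows are three-arm tests, the two sections agree and 0.091 does not apply. The text is loose enough for this to be argued, but SAP 2.2.12.4 describes the rows as each dose against vehicle and as global over visits. Even on the three-arm reading the chain remains ungated. With EASI effective, NRS null and independent statistics, the error is 1 − (1 − 0.0486)(1 − 0.05) = 0.096, and a significant row would not say which dose beats vehicle.

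A second point is that the protocol's sequence starts with NRS and EASI, which are the co-primaries, so it may have been meant as the gate. That is fair, and any alignment should preserve it. But Protocol 12.6 and 12.9 leave the detail to the SAP, and the SAP drops it. The same delegation means the SAP order would ordinarily be followed, which softens the worry about choosing an order afterwards without removing the mismatch.

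Third, the success rule in SAP 2.2.12.1 is untouched. It needs both co-primaries, and its worst simulated error is 0.0486. In a Phase IIb study the damage is confined to secondary and exploratory claims. That limits the consequence, but the SAP still makes an explicit statement of error control that its rule does not meet.

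Fourth, 0.091 assumes equal variances, and the planning SDs give 0.083 to 0.088. The large overall figure needs EASI effective and NRS null; under the global null the total is only 0.092 to 0.095.

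**Conclusion.** The concern holds. As written, the hierarchy does not control the overall type I error at 5%. At a single null step shared by both doses the error is about 0.09 (0.083 to 0.091 for correlations between 0.72 and 0.5). Over the co-primaries and row 1 together it reaches 0.111 to 0.135 when EASI responds and NRS does not. The level and the missing gate each break control on their own, and no reading of global restores it.

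These figures assume normal test statistics, a shared vehicle arm, assumed endpoint correlations of 0 to 0.8, and no effect of the interim analysis, which is a separate matter. The co-primary conclusion is not affected.

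**What to change.** In SAP 2.2.12.4:

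- Test each dose's chain at two-sided 0.026.
- Let a dose enter its chain only if it rejected both NRS and EASI at Week 8 at 0.026.
- Call a row significant only if it and every earlier row for that dose have p < 0.026.
- State that each row compares one dose with vehicle over the named visits, so that global can no longer be read as a three-arm test.

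Use one order in both documents. The simplest course is to bring Protocol 12.9.2 into line with Table 2, with the two co-primaries stated explicitly at its head. Settle this before unblinding.

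In the scenarios run, this brings the simulated error to at most 0.049. One refinement is worth knowing. If the first null steps of the two doses are different, unrelated endpoints, 0.026 each gives up to 1 − 0.974² = 0.0513. Using 0.025 per dose throughout would be strictly safe (0.025 + 0.025 = 0.05), and the co-primary sample size would be 100 (NRS) and 101 (EASI) per arm.

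The cost is SAP wording, a protocol clarification, and the fall in power for secondary tests from 80% to about 72%. No change to data collection or to the planned sample size is needed at 0.026.

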2.2.13 Safety Analyses

All subjects enrolled in the study who received at least one dose of the medication will be included in the safety analysis (i.e. Safety Analysis Set).

2.2.13.1 Extent of Exposure

Treatment duration is defined as 8 weeks (Day 56 \pm 2 days). The date of the first and last applications of study medication will be collected from information recorded on the study drug admin page of the eCRFs. Study medication is to be applied twice daily.

Extent of exposure to study medication will be tabulated by treatment group by 2-week intervals. The number of applications of study medication will be summarized by treatment group by each 2-week interval only for those subjects who returned to the clinic for each interval. The expected number of applications per 2-week intervals is 14, based on twice daily dosing. Compliance will be measured by calculating the number of applications/expected number of applications *100 and presented by treatment group for each interval.

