## 6 STUDY DESIGN

### 6.1 General

[figure not shown]
This is a randomised, vehicle-controlled, double-blind, parallel group, multi-centre Phase IIb study to investigate the efficacy of topically administered DS107 cream and the dose-response relationship between DS107 cream and vehicle cream in AD patients 18 years and older.

It is planned that approximately 300 patients, 100 patients per treatment group, with mild to moderate AD will be included in this study. All patients will sign an informed consent and undergo screening for study eligibility. Patients will be randomized (1:1:1) at baseline visit to either receive 5% DS107 cream, 1% DS107 cream or vehicle cream twice daily for 8 weeks.

Patients will come to the clinic on 7 occasions: at Screening/Visit 1, Baseline/Visit 2, Week 2/Visit 3, Week 4/Visit 4, Week 6/Visit 5, Week 8/Visit 6 (end of treatment) and Week 10/Visit 7 (follow-up). Early termination visits will be recorded for patients who withdraw from the study early. All patients will exit the study at the Week 10 visit. At the screening visit, after giving informed consent to participate, patients will be assessed using the screening examinations. Patients who meet the inclusion criteria and who do not meet the exclusion criteria will be enrolled.

A schematic diagram of the overall timeframe of the study is given in Figure 2.

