### 8.2.3 Baseline (Visit 2)

Patients will attend the investigational site at Visit 2 when the following procedures/assessments will occur.

- Verification of inclusion/exclusion criteria (Sections 7.2 & 7.3)
- Hanifin and Rajka criteria review (as detailed in Section Appendix 2 (15.2))
- Patient randomisation (as detailed in Section 10.5)
- Samples for clinical laboratory safety tests (haematology, urinalysis and serum biochemistry as detailed in Section 9.2.4)
- Biomarker sampling (as detailed in Section 9.2.6)
- Vital signs (blood pressures, heart rate and body temperature), as detailed in Section 9.2.3)
- Physical examination (as detailed in Section 9.2.2)
- Dispense study drug
- Dispense patient compliance log
- Study drug administration (on site) (as detailed in Section 10.3)
- Investigator's Global Assessment (IGA) (as detailed in Section 9.1.1)
- Body Surface Area (BSA) (as detailed in Section 9.1.4)
- Eczema Area and Severity Index (EASI) (as detailed in Section 9.1.2)
- NRS pruritus assessment (as detailed in Section 9.1.3)
- Dermatology Life Quality Index (DLQI) Questionnaire (as detailed in Section 9.1.5)
- Patient Orientated Eczema Measure (POEM) (as detailed in Section 9.1.6)
- Patient Global Impression of Severity Questionnaire (PGI-S) (as detailed in Section 9.1.7)
- Patient Global Impression of Change Questionnaire (PGI-C) (as detailed in Section 9.1.8)
- Concomitant medication assessment (as detailed in Section 9.2.9)

If all study entry criteria are satisfied the Investigator will randomize the patient and provide the patient with six tubes of the designated DS107 or vehicle cream from one of the patient treatment packs available at the site (allocated via the central randomization).

The first application of DS107 or vehicle cream will be carried out at site once all baseline assessments have been completed. The patient will carry out their second application of DS107 or vehicle cream in the evening of Day 0.

Patients will be given a compliance log to document application of the DS107 or vehicle cream. Clinical staff will explain to the patient how to use the compliance log to document IMP application compliance.

**All dispensed DS107 cream and vehicle cream should be weighed (tube only, without the outer carton but including the tube lid) upon dispensing.**

An NRS for the assessment of pruritus will be captured on a daily basis from baseline through to the follow up visit.

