### **8.2.6 Week 6 (Visit 5)**

Patients will return to the investigational site at Week 6/Visit 5. Patients should not apply DS107 or vehicle cream on the morning of Visit 5.

For accountability purposes, patients will be required to bring both the used and unused DS107/vehicle cream supplied at Visit 4. Patients will be required to provide the patient compliance log for confirmation of compliance.

The following procedures/assessments will occur:

- Vital signs (blood pressures, heart rate and body temperature) (as detailed in Section 9.2.3)
- Physical examination (as detailed in Section 9.2.2)
- Dispense study drug
- Collect study drug
- Dispense patient compliance log
- Collect and review patient compliance log
- IMP accountability (as detailed in Section 10.6)
- Study drug administration (on site) (as detailed in Section 10.3)
- Investigator's Global Assessment (IGA) (as detailed in Section 9.1.1)
- Body Surface Area (BSA) (as detailed in Section 9.1.4)
- Eczema Area and Severity Index (EASI) (as detailed in Section 9.1.2)
- NRS pruritus assessment (as detailed in Section 9.1.3)

- Dermatology Life Quality Index (DLQI) Questionnaire (as detailed in Section 9.1.5)
- Patient Orientated Eczema Measure (POEM) (as detailed in Section 9.1.6)
- Patient Global Impression of Severity Questionnaire (PGI-S) (as detailed in Section 9.1.7)
- Patient Global Impression of Change Questionnaire (PGI-C) (as detailed in Section 9.1.8)
- Concomitant medication assessment (as detailed in Section 9.2.9)
- AE assessment (as detailed in Section 11)

The DS107 or vehicle cream will be returned and six tubes of DS107 or vehicle cream will be supplied to the patient. The cream will continue to be applied twice-daily. The patient compliance log will be provided to the patient who will be instructed to complete this as before.

**All dispensed DS107 cream and vehicle cream should be weighed (tube only, without the outer carton but including the tube lid) upon dispensing and again upon return of product.**

An NRS for the assessment of pruritus will continue to be captured on a daily basis from baseline to the follow up visit.

On completion of this visit, patients will be advised that they will be required to return to the investigational site at Visit 6 and to bring with them the unused DS107/vehicle cream, the used DS107/vehicle cream, and the patient compliance log. Patients should not apply DS107 or vehicle cream on the morning of their return site visit (Visit 6).

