### **8.2.7 Week 8 (Visit 6) / End of Treatment or Early Termination**

Patients will return to the investigational site at Visit 8. **The last administration of DS107/vehicle cream should be made the evening before Visit 6.**

For accountability purposes, patients will be required to bring both the used and unused DS107/vehicle cream supplied at Visit 5. Patients will be required to provide the patient compliance log for confirmation of compliance.

The following procedures/assessments will occur:

- Samples for clinical laboratory safety tests (haematology, urinalysis and serum biochemistry as detailed in Section 9.2.4)
- Biomarker sampling (as detailed in Section 9.2.6)
- Vital signs (blood pressures, heart rate and body temperature), as detailed in Section 9.2.3)
- Physical examination (as detailed in Section 9.2.2)
- Collect study drug
- Collect and review patient compliance log
- IMP accountability (as detailed in Section 10.6)
- Investigator's Global Assessment (IGA) (as detailed in Section 9.1.1)
- Body Surface Area (BSA) (as detailed in Section 9.1.4),
- Eczema Area and Severity Index (EASI) (as detailed in Section 9.1.2)
- NRS pruritus assessment (as detailed in Section 9.1.3)
- Dermatology Life Quality Index (DLQI) Questionnaire (as detailed in Section 9.1.5)
- Patient Orientated Eczema Measure (POEM) (as detailed in Section 9.1.6)
- Patient Global Impression of Severity Questionnaire (PGI-S) (as detailed in Section 9.1.7)
- Patient Global Impression of Change Questionnaire (PGI-C) (as detailed in Section 9.1.8)
- Concomitant medication assessment (as detailed in Section 9.2.9)
- AE assessment (as detailed in Section 11)

The DS107 or vehicle cream will be returned. No further DS107 or vehicle cream or patient compliance log will be issued. Following completion of the study assessments at this visit, there will be continued study restrictions in line with those described in section 9.2.9 and 9.2.10.

An NRS for the assessment of pruritus will continue to be captured on a daily basis from baseline to the follow up visit.

On completion of this visit, patients will be advised that they will be required to return to the investigational site at Visit 7 to assess any AEs since this visit, and conduct safety and efficacy assessments.

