## 10.3 Dosage and Administration

IMP at dose strengths of 5% and 1% DS107 cream or vehicle cream will be topically applied liberally to all affected or commonly affected areas twice daily (morning and evening) by the patients. **The last study drug application should occur on the day preceding Week 8 (Visit 6) /early termination (ET) visit.** Patients will be randomized to one of the three treatment groups in a 1:1:1 ratio:

- Treatment group A: 1% DS107 cream applied topically to all affected or commonly affected areas twice-daily for 8 weeks

- Treatment group B: 5% DS107 cream applied topically to all affected or commonly affected areas twice-daily for 8 weeks
- Treatment group C: Vehicle cream applied topically to all affected or commonly affected areas twice-daily for 8 weeks

An area for treatment will be defined at study start and DS107 or vehicle cream will be applied to all that area (and any newly affected areas) for the complete 8 week duration. Emollients can be applied to other areas of dry skin not in the defined treatment area.

DS107 or vehicle cream will not be applied on the morning of clinic visits 3, 4, 5, and 6 (will be applied as soon as all of the efficacy assessments are complete during the clinic visit). To maintain the blind throughout the study, the DS107 cream and vehicle cream will be identical in appearance.

If a patient misses one application of the study product they should apply the study product as usual at the time of the next scheduled application. Patients should remember to note the missed application in the Patient Compliance Log.

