2.2.3 Dose Regimen

The following three formulations have identical appearance: 1% DS107 cream, 5% DS107 cream and Vehicle cream in a 1:1:1 ratio, respectively. The medication assigned by randomization will be topically applied liberally by the patients to all affected or commonly affected areas twice daily (morning and evening) for 8 weeks. Tabulations of exposure to study medication are described in Section 2.2.13.1, Extent of Exposure. Details of study medication use will be provided in a subject data listing.

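### No by-arm summary of the amount of cream used is planned: the SAP reports exposure as application counts, although the amount per application is not set and tubes are to be weighed

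*SAP*

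**What the plan says.** **Amount applied.** Protocol 10.3 says the cream "will be topically applied liberally to all affected or commonly affected areas twice daily (morning and evening) by the patients". SAP 2.2.3 agrees: "The medication assigned by randomization will be topically applied liberally by the patients to all affected or commonly affected areas twice daily". Neither gives grams or any other unit per application. Entry requires at least 5% BSA with no upper limit (Protocol 7.2), and skin that becomes affected later is also treated (Protocol 10.3).

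**Supply and weighing.** At baseline the site is to "provide the patient with six tubes of the designated DS107 or vehicle cream" (Protocol 8.2.3) and to weigh it. Six more tubes follow at each of Visits 3, 4 and 5, where the visit sections call for weighing "upon dispensing and again upon return of product". At Visit 6 the text reads: "The DS107 or vehicle cream will be returned. No further DS107 or vehicle cream or patient compliance log will be issued" (Protocol 8.2.7). That section lists IMP accountability but does not mention weighing.

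**Exposure analysis.** SAP 2.2.13.1 states: "The number of applications of study medication will be summarized by treatment group by each 2-week interval", limited to patients who came back for that interval. Compliance is the count divided by an expected count, times 100, and the expected count per two weeks is given as 14. Dates of first and last application are also collected. Tube weight and grams appear nowhere in the SAP. SAP 2.2.3 promises a patient listing of medication use without saying what it will contain.

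**Aim.** Protocol 6.1 includes among the purposes "the dose-response relationship between DS107 cream and vehicle cream in AD patients 18 years and older", and Protocol section 3 calls the trial dose-finding.

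**The concern.** When the patient chooses how much to apply, an application is an adherence event and not a unit of dose. Two arms can show the same counts and the same compliance while one uses much more cream than the other. The protocol asks sites to do the work that would reveal this, and no planned summary uses the result.

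Two readings of the data depend on it. One is the 1% versus 5% comparison: its nominal fivefold contrast in amount of DS107 holds only if both arms use similar grams. The other is safety, where a difference between arms, or the planned pooling of 1% and 5% (SAP 2.2.13.2), is easier to interpret when the amount used is known.

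**Working it through.** **Step 1. Reproduce the SAP's own figure.** The inputs are two applications a day and a 14-day interval (SAP 2.2.13.1).

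- Expected count = 2 × 14 = 28. The SAP states 14, so the figure does not reproduce.
- Leaving out the clinic-visit morning does not explain it. Protocol 10.3 has that application made after the efficacy assessments, and one missed application would not halve the count. Fourteen corresponds to one application a day.
- Over eight weeks: 2 × 56 = 112 = 4 × 28.
- Compliance as written, full adherence: 28 / 14 × 100 = 200%. Half adherence: 14 / 14 × 100 = 100%.

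**Step 2. What an application count leaves open.** The documents give no tube weight and no usage data. I assume 1 to 10 g per application, purely to show a range, and read the labelled percentages as grams of DS107 per 100 g of cream.

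- Cream per two weeks = 28 × grams per application.
- Nominal DS107 = cream × 0.01 or × 0.05.

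| Assumed g per application | Applications | Cream, g | DS107 at 1%, g | DS107 at 5%, g |
|---|---|---|---|---|
| 1 | 28 | 28 | 0.28 | 1.4 |
| 3 | 28 | 84 | 0.84 | 4.2 |
| 5 | 28 | 140 | 1.4 | 7.0 |
| 10 | 28 | 280 | 2.8 | 14.0 |

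The count is the same in every row, while the amount varies tenfold within each arm.

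**Step 3. At arm level.** Let r be mean grams in the 5% arm divided by mean grams in the 1% arm. The ratio of mean nominal DS107 is 5 × r.

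- r = 1: the ratio is 5.
- r = 0.6 (illustrative, 40% less cream in the 5% arm): the ratio is 5 × 0.6 = 3.
- For the ratio to fall to 1, r would have to be 1/5, and nothing in the documents points to that.

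Application counts could be identical in all three cases.

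**Step 4. Would the weights cover all eight weeks?**

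| Visit | Tubes dispensed | Weighing in that visit's section |
|---|---|---|
| 2 | 6 | at dispensing |
| 3, 4, 5 | 6 each | at dispensing and on return |
| 6 | none; last 6 returned | not mentioned |

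Per patient, 4 × 6 = 24 tubes are dispensed, and 6 / 24 = 25% come back at Visit 6. The Visit 5 sentence covers all dispensed cream and can be read to include these tubes, so the Visit 6 text is ambiguous. If it is read the other way, Weeks 6 to 8, which end at the primary time point, have no net weight.

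**Step 5. What is not affected.** No test, sample size or decision rule in either document uses the amount of cream.

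**The case against.** The strongest answer is that nothing confirmatory depends on this. Each concentration is compared with vehicle as randomised, and that comparison is valid however much cream patients choose to use. The SAP calls 1% versus 5% descriptive (2.1 and 2.2.8). Dose is defined by concentration. Grams used is a post-randomisation quantity: patients whose skin clears may use less, so it cannot cleanly explain a flat dose-response. All of that stands. It makes the table supportive, but does not make a count an adequate measure of amount.

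A reader might infer more than the documents support:

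- **That amount used will never be reported.** The listing promised in SAP 2.2.3 could carry tube weights. What is missing is a summary by arm.
- **That a flat or reversed 1% versus 5% result could not be interpreted.** It would be harder to interpret, but the comparisons with vehicle would still answer the main question.
- **That skin area can cancel the dose contrast.** At equal grams per %BSA, a 1% patient with 25% BSA and a 5% patient with 5% BSA receive the same total (25 × 1 = 5 × 5). Yet drug per unit of skin still differs fivefold, and these are two chosen patients, not arms. Baseline BSA is already compared by arm (SAP 2.2.1).
- **That one cream will be used sparingly because it stings.** Phase I saw no clinically relevant skin reactions, Phase IIa adverse events were similar to vehicle, and the vehicle differs only by the active and added water.
- **That the protocol omits weighing at Visit 6.** It is unclear there, for the reason in Step 4.

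It is also fair to say that the data may not be ready to use. Protocol 12.10 sends evaluations to the eCRF in general terms, but no document says tube weights are entered.

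**Conclusion.** The point holds as a gap in the exposure summary. The plan leaves the amount per application open, asks for tubes to be weighed, and then reports exposure by arm in a form that cannot reflect amount. Its size cannot be computed, because the documents give no tube weight or usage. The tenfold range and the 5-to-3 shift rest on assumed values and show only what a count would miss. Weight lost from a tube measures cream used, not drug absorbed. The consequence is limited to the descriptive 1% versus 5% comparison and the reading of safety differences.

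The expected count of 14 is a separate, definite error in the same section. It contradicts the twice-daily basis stated beside it and doubles every compliance percentage relative to a count of 28.

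**What to change.** **SAP 2.2.13.1.** Add one table by arm on the Safety Set:

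- grams used per two-week interval and in total (dispensed minus returned weight);
- grams per day;
- grams per day per %BSA, stating which BSA reading is the denominator. Baseline has the merit that entry keeps it at 5% or above and treatment cannot change it;
- nominal DS107 amount (grams × labelled concentration) as a secondary line;
- the number of intervals with unreturned or unweighed tubes, and how they are handled.

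Label the table supportive, because use is determined after randomisation. Keep application counts as the adherence measure, and reconcile the expected 14 with the twice-daily basis (2 × 14 = 28).

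**Data capture.** Confirm that tube weights are recorded in the eCRF. If they are not, add the fields or arrange a transfer from site accountability records.

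**Protocol 8.2.7.** Restate that returned tubes are weighed at Visit 6, so that Weeks 6 to 8 are not lost.

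**Cost.** One more table, one protocol sentence and a check of the eCRF, with more work if weights are not yet captured. Some intervals will be missing where tubes are not returned. No dose, schedule or test changes.
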